### 7.1. Inclusion Criteria

Patients are eligible to be included in the study only if they meet **all** of the following criteria:

- [1] are a male or a female between ages 10 to 17 years, inclusive. The number of patients  $\geq 17$  years of age will be limited to no more than 10% of patients in each treatment arm
- [2] have a history of type 2 diabetes with the original diagnosis based on at least one American Diabetes Association (ADA) diagnostic criteria (Section 7.1.1)
- [3] have been treated with metformin, an SU, or both metformin and an SU (with or without diet and exercise), for at least 3 months or are naïve to anti-diabetes agents and being treated with diet and exercise alone. The dose of oral agent(s) should be stable for the 30 days prior to the screening visit
- [4] have fasting C-peptide  $>0.6$  ng/mL
- [5] have no antibodies to glutamic acid decarboxylase (GAD65) or islet cell antigen (ICA512)
- [6] have HbA1c between 6.5% and 10.5%, inclusive
- [7] present an appropriately signed assent form
- [8] a parent or adult guardian agrees in writing to participate in the patient's treatment by signing a consent form
- [9] both the patient and parent or responsible adult guardian are able to understand and comply with a lifestyle modification program
- [10] the investigator determines that patient and parent or responsible adult guardian are able to fully participate in and likely to complete the trial.

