1.3 Number of patients

Approximately 195 patients diagnosed with type 2 diabetes were planned to be enrolled. Approximately 65 patients were to be randomized to receive placebo and 130 patients were to be randomized to receive exenatide (65 per exenatide treatment arm). A sample of 65 patients per treatment arm would provide >95% power to reject the null hypothesis of no difference among treatments assuming true mean changes in HbA1c of -0.7, -0.5, and 0 for patients receiving exenatide 10 µg twice daily, exenatide 5 µg twice daily, and placebo twice daily, respectively (based on results of previous Studies 2993-112, CCI, H8O-MC-GWAA, H8O-MC-GWAD). This power computation also assumes a common standard deviation of 1.0% and a two-sided significance level of 0.05. Assuming the same true mean changes in HbA1c, common standard deviation, and two-sided significance level, 65 patients per treatment arm would also provide >95% power to detect a difference between 10 µg exenatide twice daily and placebo

treatments, and 80% power to detect a difference between 5 µg exenatide twice daily and placebo with a Fisher Protected Testing procedure (Hayter 1986).

Due to an approximate 23% discontinuation rate in the exenatide arms (based on results from 2993-112), 65 patients randomized per treatment arm would be enough to observe 50 completers per treatment arm. Patients will be eligible to participate if they are not achieving adequate glycemic control (i.e. HbA1c at screening is 6.5% to 10.5%, inclusive) with metformin, an SU, or metformin and an SU, or diet and exercise only. Patients will be stratified to treatment assignment based on diabetes therapy at enrolment and screening HbA1c. The three-arm design was intended to allow comparison of exenatide at doses of 5 µg twice daily and 10 µg twice daily with placebo twice daily.

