Due to the availability of other more conveniently administered therapies e.g. oral, once daily (QD), or once weekly (QW), recruitment to this study has been slow/difficult despite extensive efforts by the sponsor. The planned number of patients will take unreasonably long to recruit so a decision was made with agreement by the European Medicines Agency and Food and Drug Administration to stop recruitment and to pool patients from both exenatide arms and compare the pooled arm with placebo. With a total of 122 patients randomized (Total EBID:Placebo 2:1), the study should have approximately 87% power to detect a difference between Total EBID and placebo assuming the true mean changes in HbA1c are -0.7, -0.5, and 0 for patients receiving exenatide 10 µg BID, exenatide 5 µg BID, and placebo BID, respectively. The combined effect of the Total EBID doses compared to placebo (mean difference) is assumed to be -0.6 with a common standard deviation of 1% at the 5% significance level without consideration of patient discontinuation and impact on effect size. An assumed effect size of -0.455 was considered in power calculation.

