4.1.2 Hypothesis testing significance level

Statistical tests, where performed, will be conducted at a 2-sided significance level of 5%. Where appropriate, model-based point estimates, together with their 95% confidence intervals will be presented along with the 2-sided p-values for the tests.

No adjustments for multiplicity (including hierarchical testing) will be made for the primary, secondary and exploratory variables.

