4.2.4.4 Analysis of secondary variables

Summary statistics and frequency tables will be provided for all secondary endpoints by visit and treatment for the Full analysis set during the treatment period (see Section 3.6.5 for treatment period definition), unless otherwise stated.

As for the primary analysis, data including the ED visit where applicable will be included in the MMRM/ANCOVA and CMH analysis for secondary analysis variables. Data collected from an ED visit will be mapped to the next closest scheduled visit. For patients who initiate rescue medication and continue study participation, data collected after the initiation of rescue medication will be excluded from analyses. Data collected after discontinuation of IP will be excluded from analyses for all other secondary efficacy endpoints.

Change in HbA1c from baseline Visit 3 (Week 0) to each intermediate visit

The MMRM method for change in HbA1c will be used until Week 28 and to each intermediate visit, using the Evaluable analysis set, which is the same approach as stated in Section 4.2.4.2.

The least squares mean (LSM) change from baseline and SE bar by visit will be presented in a figure by treatment group. The p-value for the difference between treatment groups by visit will also be provided in the figure.

Actual, change and percent change from baseline values of HbA1c will be summarized using descriptive statistics by visit and treatment group for the Evaluable analysis set. OC summaries will be provided.

HbA1c measures will be listed.

Proportions of patients achieving HbA1c goals

Proportions of patients having HbA1c goals of <7%, ≤6.5%, and <6.5% at Week 28 will be compared between treatments (Total EBID vs. PBO) using the Evaluable analysis set via the CMH procedure, in which screening HbA1c strata and background diabetes therapy strata will serve as the stratification factors.

A bar chart of the percentage of patients achieving HbA1c goals of <7%, ≤6.5%, and <6.5% by treatment group will be provided along with p-values.

The number and percentage of patients having HbA1c goals of <7%, ≤6.5%, and <6.5% will be summarized by visit and treatment group for the Evaluable analysis set.

Any Evaluable patient without HbA1c value at the endpoint will be considered as not achieving HbA1c goal at endpoint. The denominator will be the total number of Evaluable patients in the treatment group, and the numerator will be the number of patients achieving HbA1c <7%, ≤6.5%, and <6.5%.

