6 CHANGES OF ANALYSIS FROM PROTOCOL

The CSP does not specify eGFR as an endpoint, nor is it provided by the laboratory. However, since eGFR could provide important information it will be derived and analyzed as stated in Section 4.2.4.5 of this SAP.

In addition to the protocol-specified analysis, hypoglycemia will be summarized by baseline sulfonylurea use (yes/no) and treatment.

No Generalized Linear Mixed Model (GLMM) analysis will be done using the binary HbA1c outcome (achieved vs. not achieved HbA1c goal) as the dependent variable.

No per-protocol analysis for supportive analyses will be done.

Due to the lack of data and extent of missing data, efficacy analyses will be pooled across the 5 µg and 10 µg twice daily exenatide doses for statistical testing (Total EBID). Thus, the Fisher Protected Testing produced for the primary analysis will not be required.

For the analysis of SMBG, pre and post measurement for the same meal (lunch/dinner) is changed to be generically 2 main meals (i.e. allowing breakfast) and changed to allow data from consecutive days to be used (as many patients had only consecutive days data recorded).

Due to lack of data, plasma exenatide concentrations and antibodies will only be listed.

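### The HbA1c goal tests do not adjust for continuous baseline HbA1c, at a modest cost in power, and the <7% result does not separate patients who entered already below 7%.

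*SAP*

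**What the plan says.** - **Goals and test.** SAP section 4.2.4.4: "Proportions of patients having HbA1c goals of <7%, ≤6.5%, and <6.5% at Week 28 will be compared between treatments", by a CMH procedure stratified by screening HbA1c stratum and background therapy (four levels). The HbA1c cut is 8%. The denominator is every Evaluable patient in the arm, and a missing Week 28 value counts as failure.
- **Sensitivity analysis.** The same section repeats the CMH on data imputed under the pattern mixture model.
- **Entry.** Protocol section 7.1 requires patients to "have HbA1c between 6.5% and 10.5%, inclusive". SAP section 1.3 applies this range at screening.
- **Dropped model.** SAP section 6: "No Generalized Linear Mixed Model (GLMM) analysis will be done using the binary HbA1c outcome".
- **Primary analysis, for contrast.** The MMRM in SAP section 4.2.4.2 includes continuous baseline HbA1c and its interaction with week.
- **Status.** These are secondary endpoints, tested at two-sided 5% with no multiplicity adjustment (SAP section 4.1.2). A bar chart with p-values is planned.

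**The concern.** Whether a patient falls below a fixed threshold depends heavily on where that patient started. The goal test controls for this only through a two-level screening stratum, so a patient at 6.5% shares the lower level with one at 8.0%. The plan already uses the measured baseline for the continuous form of the same variable, so leaving it out of the binary form discards information in hand. With 122 patients, that matters.

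The second issue is what the percentage means. For <7%, the entry range and the goal overlap. The reported proportion combines patients brought below 7% with patients who were there at the start, and the SAP does not clearly provide a display that separates them.

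**Working it through.** **1. The plan's own figure.** The documents give no power or response rate for the goals. The only power statement concerns the primary endpoint: "With a total of 122 patients randomized (Total EBID:Placebo 2:1), the study should have approximately 87% power", where the difference "is assumed to be -0.6 with a common standard deviation of 1% at the 5% significance level".

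- Arms: 122 × 2/3 = 81.33 and 122 × 1/3 = 40.67.
- SE = 1.0 × √(1/81.33 + 1/40.67) = 0.192.
- Power = Φ(0.6/0.192 − 1.96) = Φ(1.16) = 87.8% (noncentral t: 87.3%). The stated 87% is reproduced.
- The same paragraph adds: "An assumed effect size of -0.455 was considered in power calculation". That value gives Φ(0.455/0.192 − 1.96) = Φ(0.41) = 65.9%, so 87% belongs to −0.6. I use −0.6 below; a smaller effect would lower every power shown.

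**2. Overlap, from the documents alone.** Screening values of 6.5% to 6.9% are eligible and already meet <7%. For ≤6.5% the only eligible value at goal is exactly 6.5%. For <6.5% there is none.

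**3. Size, by simulation.** From the SAP: 122 patients, 2:1, effect −0.6, SD of change 1.0, and missing counted as failure at 0% or 23% (the discontinuation rate in SAP section 1.3, applied here to both arms). Assumed, because the documents do not give them:

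- screening HbA1c truncated normal on 6.5–10.5 (location/scale before truncation 7.5/1.2, 8.2/1.2 or 8.5/1.0) or uniform;
- baseline = screening + N(0, 0.3), values rounded to 0.1;
- regression-to-the-mean slope 0 or 0.3;
- background mix 15/70/3/12% (naïve, metformin, SU, both).

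There were 1,500 trials per scenario. The Monte Carlo SE of a power near 40% is √(0.4 × 0.6/1500) = 1.3 points. All methods were run on the same simulated trials.

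Goal <7%. Power in %, without missing data / with 23% missing; responder share without missing data:

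| Screening HbA1c | Slope | At goal at baseline | Their share of responders | Planned CMH | CMH + at-goal stratum | CMH, at-goal excluded | Logistic score test, continuous baseline |
|---|---|---|---|---|---|---|---|
| 8.2/1.2 | 0 | 8.9% | 25.5% | 37.7 / 25.2 | 36.8 / 25.5 | 33.1 / 23.0 | 44.5 / 31.5 |
| 8.2/1.2 | 0.3 | 8.9% | 23.6% | 44.3 / 31.1 | 43.2 / 30.1 | 36.3 / 25.5 | 47.9 / 34.3 |
| 7.5/1.2 | 0 | 16.2% | 34.1% | 46.8 / 31.5 | 47.9 / 30.4 | 37.6 / 27.3 | 53.0 / 34.9 |
| 7.5/1.2 | 0.3 | 16.2% | 31.2% | 56.1 / 39.4 | 55.7 / 38.2 | 45.5 / 31.7 | 60.4 / 41.7 |
| 8.5/1.0 | 0 | 4.9% | 17.5% | 37.3 / 27.3 | 37.1 / 26.5 | 35.1 / 24.7 | 41.9 / 29.5 |
| 8.5/1.0 | 0.3 | 4.9% | 16.0% | 39.3 / 29.4 | 38.0 / 28.3 | 35.9 / 26.0 | 43.7 / 31.2 |
| uniform | 0 | 11.5% | 35.2% | 34.7 / 23.4 | 34.9 / 22.6 | 27.2 / 19.2 | 41.1 / 27.3 |
| uniform | 0.3 | 11.5% | 34.1% | 40.2 / 28.3 | 38.5 / 26.6 | 30.5 / 20.4 | 44.9 / 31.0 |

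- **Continuous baseline** adds about 2 points (31.2 − 29.4 = 1.8) to 7 points (44.5 − 37.7 = 6.8).
- **An at-goal stratum** changes power by −2 to +1 points.
- **Excluding at-goal patients** lowers power by 2 to 11 points (for example 56.1 − 45.5 = 10.6).
- **Other goals.** For <6.5%, continuous baseline adds about 1 to 6 points. After drift between screening and Visit 3, about 1% to 5% of patients are at ≤6.5% at baseline and about 1% to 3% at <6.5%.
- **Type I error** of the planned CMH is 3.0% to 6.1% over all null scenarios, which is nominal or slightly conservative within simulation error.

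**4. Choice of test for the adjusted model.** Further simulations on similar assumptions, for <7%:

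| Adjusted test | Gain over CMH (points) | Type I error |
|---|---|---|
| Score test | 3 to 7 | 4.6–5.8% (baseline + treatment); 5.0–6.2% (with pooled background terms) |
| Unpenalised likelihood ratio, baseline + treatment | 3 to 8 | 4.7–6.5% |
| Unpenalised likelihood ratio, with four-level background therapy | 6 to 9 | 5.7–7.4% |

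The largest gain comes with the most inflated error rate, so part of it is not real. Those runs put 7% to 17% of patients below 7% at baseline.

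**The case against.** The strongest defence is that the goal endpoint is defined as status at Week 28. Randomisation is stratified by screening HbA1c and background therapy, the CMH holds its level, and the primary analysis already adjusts for baseline. On that view nothing is invalid and the endpoint is secondary. All of this stands, and it rules out several stronger readings that a reader might infer:

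- **That the CMH controls only for the 8% cut.** Background therapy is also a stratification factor. The 8% cut is the only control on HbA1c level.
- **That patients already at goal cause the power loss.** The table shows the reverse: removing them lowers power and giving them a stratum gains nothing. The low absolute power comes mainly from dichotomising, the sample size and counting missing as failure.
- **That all three goals overlap the entry range materially.** Only <7% does.
- **That a patient may enter at 6.3%.** SAP Table 1 sets ±0.2% as a threshold for listing a deviation. Protocol section 7.1 still requires 6.5%, and section 7.3 gives a patient at 6.3% or 6.4% one rescreen, which must return an eligible value.
- **That about 10 points of power are recoverable.** That exceeds what a test with acceptable type I error delivers here.
- **That no goal analysis touches measured baseline HbA1c.** The imputation model behind the sensitivity CMH includes it, though that affects only missing values. Nor do the documents say that the dropped GLMM would have adjusted for baseline, because protocol section 11.2.7 lists no covariates.

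It can also be said that at-goal counts may appear anyway. Protocol section 11.2.7 has efficacy measures summarised at baseline, and SAP section 4.2.4.4 summarises goals by visit. But SAP section 3.2 names only Week 28 and intermediate visits, so a baseline panel is arguable. Even with one, the tables would not show which Week 28 responders started at goal.

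**Conclusion.** The point holds in two separate and limited parts. First, no goal test adjusts for continuous baseline HbA1c. For <7% this forgoes roughly 2 to 8 points of power, with the score test in the lower part of that range (2 to 7). Second, the <7% percentage includes patients who began below 7%: about 5% to 17% of patients and 16% to 35% of responders. That is a matter of interpretation. The documents do not support a claim of bias, of an invalid CMH or of power lost to these patients.

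Both sizes depend on a baseline HbA1c distribution that the documents do not report, and on the assumed drift, regression slope and background mix. The existence of the overlap and the absence of the covariate do not depend on them.

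**What to change.** In SAP section 4.2.4.4, before unblinding:

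1. Keep the stratified CMH as planned.
2. Add a logistic regression for each goal on treatment, continuous baseline HbA1c and background therapy, in the same patients and with the same missing-as-failure rule. Pool the rare SU levels in advance. Name one test, score or penalised likelihood, and do not use the unpenalised likelihood-ratio test. Report a standardised difference in proportions, which matches the summary that SAP Table 3 gives for this estimand.
3. Report by arm the number at each goal at baseline.
4. Show descriptively the proportion reaching each goal among patients not at it at baseline (≥7.0% for <7%; >6.5% for ≤6.5%; ≥6.5% for <6.5%). Do not test this subset as the main comparison, because it loses patients and power.

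The cost is some SAP wording, one model and one table panel, with no new data. The downsides are a model assumption, type I error that may sit slightly above nominal at this sample size (5.0% to 6.2% in the simulations with pooled background terms), and subset percentages that will look less favourable than the all-patient ones.

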2.1.3 Full analysis set

The Full analysis set (FAS) will consist of all randomized patients who receive at least one dose of randomized study medication. Full analysis set patients will be analyzed in accordance to

their planned treatment group. This set will be used for listings and summaries of non-HbA1c efficacy data.

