2.1.4 Evaluable analysis set

The Evaluable analysis set will consist of all randomized patients who received at least 1 dose of randomized study medication and have a baseline and at least 1 post-baseline HbA1c assessment. Evaluable patients will be analyzed in accordance to their planned treatment group. This set will be used for listings and summaries of HbA1c efficacy data.

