4.1.3 Handling of missing data

4.1.3.1 Missing efficacy data

Missing data in this study may result from patients discontinuing from the study prematurely or missing intermediate visits or selected assessments while remaining on study. Every effort will be made to obtain the CSP-required data for all study assessments that are scheduled for all patients who have been enrolled. Data collected after initiation of rescue therapy will be excluded from most efficacy analyses (see Section 4.2.4 for details) and therefore these data will effectively be handled as missing in analyses. For efficacy analyses, in general missing observations will not be imputed, except those inherited from the mixed model repeated measures (MMRM) which implicitly assumes that data are missing at random (MAR).

Sensitivity of the primary analysis will be performed using pattern mixture model imputation for missing values and details of this imputation is provided in Section 4.2.4.3.

Missing at Random (MAR) refers to missingness that is independent of missing responses, conditionally on observed responses and covariates. As the imputation strategy should always consider the dropout patterns and the time-course of the efficacy measurements by treatment, the pre- and post- withdrawal values will be assessed to understand the impact of dropouts on the efficacy results. The primary efficacy endpoint of HbA1c data will be visually examined to explore the missingness patterns by (1) plotting each individual patient's HbA1c change trajectory in completers, side-by-side with those from the early study drug withdrawal, and by (2) plotting the early study drug withdrawal's last HbA1c change data, overlaid with the box plot by visit from completer population.

For categorical endpoints HbA1c goals of <6.5%, ≤6.5% and <7% at 28 weeks, any patient with missing HbA1c value at 28 weeks will be considered as failed to meet HbA1c <6%, ≤6.5% and <7%, respectively, at endpoint (28 Weeks).

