4.2.4 Efficacy analysis

4.2.4.1 Estimands

Estimands for the study are defined in Table 3. Intercurrent events (IE) that may occur during the study are receipt of rescue therapy, IP discontinuation and study withdrawal.

Table 3 Estimand framework

Estimand	Attributes			
	Population	Variable	Intercurrent event (IE) strategy	Population-level summary
Primary	Evaluable	Change in HbA1c from baseline to Week 28	All IEs: Data after event excluded. Hypothetical approach due to missing at random (MAR) assumption of MMRM analysis.	Least squares mean difference in CFBL at Week 28 between Total EBID and PBO
Sensitivity to primary	Evaluable	Change in HbA1c from baseline to Week 28	All IEs: Data after event excluded. Hypothetical approach using multiple imputation (MI) pattern mixture modelling.	Least squares mean difference in CFBL at Week 28 between Total EBID and PBO
Supplementary to primary	Evaluable	Change in HbA1c from baseline to Week 28	Rescue and IP discontinuation: Data after event included. Treatment policy approach Withdrawal from study prior to Week 28: Hypothetical approach due to MAR assumption of MMRM analysis	Least squares mean difference in CFBL at Week 28 between Total EBID and PBO

	Attributes			
Estimand	Population	Variable	Intercurrent event (IE) strategy	Population-level summary
Sensitivity to supplementary of primary	Evaluable	Change in HbA1c from baseline to Week 28	Rescue and IP discontinuation: Data after event included. Treatment policy approach Withdrawal from study prior to Week 28: Hypothetical approach using MI pattern mixture modelling	Least squares mean difference in CFBL at Week 28 between Total EBID and PBO
Secondary 1	Evaluable	Proportions of patients having HbA1c goals of <7%, ≤6.5%, and <6.5% at Week 28	All IEs: Data after event excluded. Composite approach used, with patients with missing data at endpoint treated as non-responders	Difference in proportion of responders at Week 28 between Total EBID and PBO
Sensitivity to secondary 1	Evaluable	Proportions of patients having HbA1c goals of <7%, ≤6.5%, and <6.5% at Week 28	All IEs: Data after event excluded. Hypothetical approach using MI pattern mixture modelling	Difference in proportion of responders at Week 28 between Total EBID and PBO

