As a sensitivity analysis, also in the Evaluable analysis set, the probabilities of patients reaching HbA1c targets of <7%, ≤6.5%, and <6.5% will be analyzed to Week 28 using the CMH procedure, with missing data imputed using MI pattern mixture model imputation. HbA1c and background diabetes therapy strata will serve as the stratification factors. The imputed HbA1c data for the sensitivity analysis of the primary endpoint will be used for this analysis.

Similar outputs (bar chart including p-values and summary of the numbers and percentage of patients having HbA1c goals by visit and treatment group) will be produced for the Evaluable analysis set for this sensitivity analysis.

Change in body weight, FSG and FSI from baseline Visit 3 (Week 0)

The same MMRM approach (as used for the primary analysis) will be used to analyze the change in body weight from baseline Visit 3 (Week 0) to Week 28, and each intermediate visit. Baseline body weight will replace baseline HbA1c and screening HbA1c strata will be included in these models.

Since only baseline and endpoint FSG and FSI measurements are collected, these endpoints will be analyzed by multiple imputation based on the assumption that missing data are MAR via the following steps:

Step 1: Non-monotone missing data (expected to be infrequent) will be imputed using the MCMC option of SAS PROC MI with treatment, baseline FSG/FSI, screening HbA1c strata (≤8% and >8%) and background diabetes therapy strata (drug naïve, metformin only, SU only, and metformin +SU) and value of the endpoint at each visit. This will create a monotone missing pattern in the dataset within each treatment group. This step will create 1000 imputed datasets.

Step 2: After a monotone missing pattern is created for the data, PROC MI using MONOTONE REGRESSION will be used to impute missing post-baseline values. The covariates used in the model will be treatment, baseline FSG/FSI, screening HbA1c strata (≤8% and >8%) and background diabetes therapy strata (drug naïve, metformin only, SU only, and metformin +SU) and value of the endpoint at each visit. This is MAR imputation.

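### The HbA1c-goal analysis counts a missing Week 28 value as failure only within the Evaluable set, so a dosed patient with no post-baseline HbA1c is dropped rather than counted as not at goal (low priority)

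*SAP*

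**What the plan says.** SAP 4.2.4.4 compares the proportions below 7%, at or below 6.5%, and below 6.5% at Week 28 between pooled exenatide and placebo. It uses a CMH test stratified by screening HbA1c and background therapy, in the Evaluable set. The missing-value rule is "Any Evaluable patient without HbA1c value at the endpoint will be considered as not achieving HbA1c goal at endpoint", and the denominator is fixed to match: "The denominator will be the total number of Evaluable patients in the treatment group".

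SAP 2.1.4 limits that set to randomised, dosed patients who "have a baseline and at least 1 post-baseline HbA1c assessment". SAP 2.1.3 defines the Full analysis set as all randomised patients with at least one dose, and gives it a different use: "This set will be used for listings and summaries of non-HbA1c efficacy data".

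Table 3 in SAP 4.2.4.1 also names the Evaluable population for this estimand (Secondary 1). Its strategy for all intercurrent events is "Composite approach used, with patients with missing data at endpoint treated as non-responders". The same section names study withdrawal among those events. SAP 4.1.3.1 is worded more widely: "any patient with missing HbA1c value at 28 weeks will be considered as failed to meet". It names no analysis set. The multiple-imputation check on the goals is described as "As a sensitivity analysis, also in the Evaluable analysis set" and reuses the imputed data from the primary endpoint's sensitivity analysis.

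Protocol 11.2.1 defines its analysis set as all randomised patients who took at least one dose. Protocol 11.2.7 plans the CMH test and names no narrower set. Protocol 11.2.1 also requires non-primary analysis changes, with their justification, to be described in the SAP.

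**The concern.** A post-baseline value is a practical need for a repeated-measures model of change from baseline. A rule that turns a missing value into a failure does not need one. Requiring it here creates an uneven rule: a patient who leaves after one post-baseline HbA1c is a failure, and a patient who leaves before any disappears. Both had the same intercurrent event, which the composite strategy is meant to absorb.

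The exclusion depends on something that happens after randomisation, so it can differ between arms. It always raises the responder rate of the arm it affects. Unequal loss also biases the difference, in a direction the documents do not fix. No planned goal analysis brings these patients back, because the sensitivity analysis uses the same set. SAP Section 6 records the dropped GLMM for this endpoint, but neither the change of set nor the missing-as-failure rule.

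**Working it through.** **Who is affected.** Four places in the plan bear on this.

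- Entry to the Evaluable set needs a post-baseline HbA1c assessment (SAP 2.1.4). It does not say the value must be usable. Patients whose only values are later excluded, after rescue or stopping study drug, therefore appear to stay in as failures.
- HbA1c is scheduled at Week 4 and at early discontinuation (protocol Attachment 1), and early leavers are asked back for that visit (protocol 6.1.6).
- The Week 4 window runs from Day 2 to Day 56 (SAP 4.3.1), so most early values are caught.
- Baseline is the last value on or before first dose (SAP 3.6.1), so the baseline requirement should exclude almost nobody.

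The affected group is thus dosed patients who leave before any post-baseline HbA1c and do not return. It is probably small. The documents give no count, so every figure below rests on assumed losses.

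**Effect on one arm.** With r responders among n dosed and a share e left out, all of them not at goal, the rate moves from r/n to r/[n(1 − e)], a factor of 1/(1 − e).

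| e | Factor | Shift at a 30% rate, loss in one arm only |
|---|---|---|
| 2.5% | 1.03 | 0.8 points |
| 5% | 1.05 | 1.6 points |
| 10% | 1.11 | 3.3 points |

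**Effect on the comparison.** SAP 1.3 gives 122 randomised at 2:1, taken here as 81 v 41, all dosed. Responders are assumed to be 32 v 10. The test is an unstratified Pearson chi-square without continuity correction. For example, leaving out 4 v 0 gives 32/77 − 10/41 = 41.6% − 24.4% = 17.2 points.

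| Left out (exenatide v placebo) | Difference | p |
|---|---|---|
| 0 v 0 (all dosed) | 15.1 points | 0.097 |
| 2 v 1 | 15.5 | 0.095 |
| 2 v 0 | 16.1 | 0.079 |
| 0 v 2 | 13.9 | 0.136 |
| 4 v 0 | 17.2 | 0.064 |
| 8 v 4 | 16.8 | 0.086 |
| 8 v 0 | 19.4 | 0.039 |

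Only the last row crosses 0.05. It needs 8/81 = 9.9% of one arm lost and none of the other.

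**Type I error.** This was simulated with the stratified CMH test (200,000 replicates). The true all-dosed rate was 30% in both arms and every excluded patient was a non-responder. Assumed: half the patients in each HbA1c stratum, with rates of 45% and 15%, and therapy shares of 15/70/5/10% (naïve, metformin, SU, both). With loss in one arm only, whichever arm, rejection was 5.0–5.1% at 2.5% v 0%, 5.3–5.5% at 5% v 0%, and 6.5–6.8% at 10% v 0%. With equal loss of 5% it was 4.9%. Counting all dosed patients gave 4.9–5.1%.

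**The case against.** The best defence is that the SAP is open and consistent about its sets. HbA1c data go to the Evaluable set and other efficacy data to the Full analysis set. A reader might infer a contradiction from the opening of SAP 4.2.4.4, where "frequency tables will be provided for all secondary endpoints by visit and treatment for the Full analysis set" appears as the default. The sentence goes on to allow stated exceptions, and the goals paragraph states one. Table 3 and 4.2.4.4 also agree. So the issue is the choice of set, not an inconsistency in its use. Using one population for all HbA1c analyses is a legitimate aim.

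A reader might also infer that the protocol would have counted these patients as failures. It would not. Protocol 11.2.1 allows no imputation except last observation carried forward of post-baseline values in change analyses, and 11.2.7 adds no rule for the goals. On missing data the SAP is stricter than the protocol. Nor does the broader wording of SAP 4.1.3.1 settle the matter, since it names no set.

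The affected patients should be visible. SAP 4.2.1.1 reports analysis-set counts by arm. Items 7 and 8 of SAP Table 1 make the lack of a valid baseline HbA1c, or of any valid on-treatment HbA1c, an important deviation to be listed. From the counts a reader can rebuild the crude all-dosed rates, though not the stratified CMH p-value.

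These points stand and lower the priority. They do not explain why a missing-as-failure endpoint needs a post-baseline value, or why the changes are absent from Section 6.

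**Conclusion.** The point holds as a low-priority improvement to a secondary endpoint that is tested at 5% without multiplicity adjustment (SAP 4.1.2). The planned goal analyses omit dosed patients with no post-baseline HbA1c, although the SAP's composite strategy would naturally count them as not at goal. The protocol's all-dosed set has been narrowed without being listed, and the missing-as-failure rule is a second unlisted change.

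With equal or small loss the effect is negligible. It becomes noticeable only if about a tenth of one arm is lost and little or none of the other. That rests on assumed counts, responder rates and stratum shares. The documents do not support a claim that the endpoint's conclusion is likely to change, or that the bias favours exenatide. They also give no reason, on this point, to alter the primary analysis.

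**What to change.** Run the HbA1c-goal stratified CMH test on the Full analysis set, counting every patient without a usable Week 28 value as not at goal. In the SAP:

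- change the population for Secondary 1 in Table 3;
- change the set, denominator and missing-value rule in the goals part of 4.2.4.4;
- make 4.1.3.1 agree with it by naming the set;
- exempt the goals from the limit in 2.1.3 that keeps the Full analysis set for non-HbA1c data;
- list both the analysis set and the missing-as-failure rule in Section 6, with reasons.

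Leave the Evaluable definition in 2.1.4 and the primary analysis unchanged. The multiple-imputation check on the goals may stay in the Evaluable set: it reuses the primary endpoint's imputed data, and extending it would need a separate imputation run.

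The cost is some SAP wording and a rerun of the CMH code on a slightly larger set, with no new data. The downside is slightly lower reported responder rates and a goal population that no longer matches the primary HbA1c analysis.
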